8.3.2 Direct access to source data and documents

The investigator/institution will permit trial-related monitoring, audits, IRB/IEC review and regulatory inspection, providing direct access to all related source data/documents. CRFs and all source documents, including progress notes (if applicable) and copies of laboratory and medical test results must be available at all times for review by the sponsor's clinical trial monitor, auditor and inspection by health authorities (e.g. FDA). The Clinical Research Associate/on site monitor and auditor may review all CRFs, and written informed consents. The accuracy of the data will be verified by reviewing the documents described in [Section 8.3.1](#).

8.3.3 Storage period of records

Trial site:

The trial site must retain the source and essential documents (including ISF) according to the national or local requirements (whatever is longer) valid at the time of the end of the trial.

Sponsor:

The sponsor must retain the essential documents according to the sponsor's SOPs.

8.4 EXPEDITED REPORTING OF ADVERSE EVENTS

BI is responsible to fulfil their legal regulatory reporting obligation and in accordance to the requirements defined in this CTP.

8.5 STATEMENT OF CONFIDENTIALITY

Individual subject medical information obtained as a result of this trial is considered confidential and disclosure to third parties is prohibited with the exceptions noted below. Subject confidentiality will be ensured by using subject identification code numbers.

Treatment data may be provided to the subject's personal physician or to other appropriate medical personnel responsible for the subject's welfare. Data generated as a result of the trial need to be available for inspection on request by the participating physicians, the sponsor's representatives, by the IRB/IEC and the regulatory authorities, i.e. the CA.

8.6 COMPLETION OF TRIAL

The EC / competent authority in each participating EU member state needs to be notified about the end of the trial (last subject / subject out, unless specified differently in [Section 6.2.3](#) of the CTP) or early termination of the trial.

10. APPENDICES

Not applicable.

The figure consists of a 3x3 grid of binary matrices, each represented by a 3x3 grid of black and white pixels. The matrices are arranged in three rows and three columns. The top row contains three 3x3 matrices. The middle row contains three 3x3 matrices. The bottom row contains three 3x3 matrices. The matrices are composed of black and white pixels, with some white pixels having small black dots in the center. The matrices are as follows:

- Top-left matrix:
 - Row 1: Black, Black, Black
 - Row 2: Black, White, Black
 - Row 3: Black, Black, Black
- Top-middle matrix:
 - Row 1: Black, White, Black
 - Row 2: White, White, White
 - Row 3: Black, White, Black
- Top-right matrix:
 - Row 1: Black, Black, Black
 - Row 2: Black, White, Black
 - Row 3: Black, Black, Black
- Middle-left matrix:
 - Row 1: Black, White, Black
 - Row 2: White, White, White
 - Row 3: Black, White, Black
- Middle-middle matrix:
 - Row 1: Black, White, Black
 - Row 2: White, White, White
 - Row 3: Black, White, Black
- Middle-right matrix:
 - Row 1: Black, White, Black
 - Row 2: White, White, White
 - Row 3: Black, White, Black
- Bottom-left matrix:
 - Row 1: Black, Black, Black
 - Row 2: Black, White, Black
 - Row 3: Black, Black, Black
- Bottom-middle matrix:
 - Row 1: Black, White, Black
 - Row 2: White, White, White
 - Row 3: Black, White, Black
- Bottom-right matrix:
 - Row 1: Black, Black, Black
 - Row 2: Black, White, Black
 - Row 3: Black, Black, Black

Proprietary confidential information © 2017 Boehringer Ingelheim International GmbH or one or more of its affiliated companies

The figure consists of three vertically stacked panels, each representing a different group (Group 1, Group 2, and Group 3). Each panel contains three horizontal bars, one for each category (A, B, and C). The bars are composed of black segments and white segments, with the total length of the bars increasing from Group 1 to Group 3. The segments are separated by thin vertical lines. The first panel has a total of 10 segments, the second has 11, and the third has 12. The segments are distributed as follows:

- Group 1:** Category A has 5 segments, Category B has 3 segments, and Category C has 2 segments.
- Group 2:** Category A has 6 segments, Category B has 4 segments, and Category C has 3 segments.
- Group 3:** Category A has 7 segments, Category B has 5 segments, and Category C has 4 segments.

2. LIST OF ABBREVIATIONS

Term	Definition / description
ADME	Absorption, distribution, metabolism, and excretion
ADS	Analysis dataset
AE	Adverse event
AESI	Adverse event of special interest
ALT	Alanine aminotransferase
a.m.	Ante meridiem
ANOVA	Analysis of variance
AST	Aspartate aminotransferase
AUC _{0-∞}	Area under the concentration-time curve of the analyte in plasma over the time interval from 0 extrapolated to infinity
AUC ₀₋₁₆₈	Area under the concentration-time curve of the analyte in plasma over the time interval from 0 to 168 h
BA	Bioavailability
BI	Boehringer Ingelheim
BLQ	Below the lower limit of quantification
BMI	Body mass index
CARE	Clinical data analysis and reporting environment
C _{max}	Maximum measured concentration of the analyte in plasma
CTP	Clinical Trial Protocol
CTR	Clinical Trial Report
CV	Arithmetic coefficient of variation
DBLM	Database lock meeting
DNA	Deoxyribonucleic acid
ECG	Electrocardiogram
eCRF	Electronic case report form
ES	Entered set
EudraCT	European union drug regulating authorities clinical trials
F/U	Follow-up
gCV	Geometric coefficient of variation
gMean	Geometric mean

Term	Definition / description
ICH	International Conference on Harmonisation
IPV	Important protocol violation
LLT	Lower level term
MedDRA	Medical Dictionary for Regulatory Activities
NOA	Not analysed
NOP	No peak detectable
NOR	No valid result
NOS	No sample available
PK	Pharmacokinetic(s)
PKS	PK analysis set
PV	Protocol violation
R	Reference treatment
RI	Rifampicin
RAGe	Report appendix generator
REP	Residual effect period
RPM	Report planning meeting
SAE	Serious adverse event
SD	Standard deviation
SDL	Subject data listing
$t_{1/2}$	Terminal half-life of the analyte in plasma
t_{\max}	Time from (last) dosing to the maximum measured concentration of the analyte in plasma
T	Test treatment
TS	Treated set
TSAP	Trial statistical analysis plan
ULN	Upper limit of normal range

3. INTRODUCTION

As per ICH E9, the purpose of this document is to provide a more technical and detailed elaboration of the principal features of the analysis described in the revised CTP, and to include detailed procedures for executing the statistical analysis of the primary and secondary variables and other data.

This TSAP assumes familiarity with the CTP and its amendments. In particular, the TSAP is based on the planned analysis specification as written in CTP Section 7 “Statistical Methods and Determination of Sample Size”. Therefore, TSAP readers may consult the CTP for more background information on the study, e.g., on study objectives, study design and population, treatments, definition of measurements and variables, planning of sample size, randomisation.

Study data will be stored in a trial database within the Oracle ClinicalTM system.

The statistical analyses will be performed within the validated working environment CARE, including SASTM (current Version 9.4, by SAS Institute Inc., Cary, NC, USA), and a number of SASTM-based tools (e.g., macros for the analyses of AE data or laboratory data; RAGe system for compilation/formatting of the CTR appendices).

PK parameters will be calculated using WinNonlinTM software (professional Network version Phoenix 6.3, Pharsight Corporation, Mountain View, CA 94041-1530, USA).

4. CHANGES IN THE PLANNED ANALYSIS OF THE STUDY

All analyses described in this TSAP are in accordance with the statistical methods described in the CTP.

Section 5.2.1 of the CTP specifies that safety and tolerability will be assessed based on AEs, safety laboratory tests, vital signs, 12-lead ECG, and physical examination. Because of the requirements for registry and results disclosure ([1](#)) [001-MCS-00-131_RD-03], one particular endpoint out of these parameters had to be defined as safety endpoint of this trial. Note that this is not a deviation from the CTP, as all planned analyses of safety and tolerability will be conducted as planned. In order to fulfil the requirements for registry and results disclosure, the frequency [N (%)] of subjects with drug related AEs is defined as safety endpoint in [Section 5.3.1](#) of this TSAP, while all other parameters for assessing safety and tolerability are defined as further criteria of interest.

The CTP states in Section 7.3.3 that events occurring in a certain phase of the study will be summarized as 'post-treatment' events. The BI corporate guideline 001-MCG-156 ([6](#)) had been updated to replace the term 'post-treatment' by 'follow-up'. This TSAP follows the updated terminology from the BI corporate guideline.

5. ENDPOINTS

5.1 PRIMARY ENDPOINTS

Primary PK endpoints will be defined as in Section 5.5.1.1 of the CTP:

- AUC_{0-168} of BI 425809 in plasma with and without co-administration of rifampicin (area under the concentration-time curve of the analyte in plasma over the time interval from 0 to 168 h)
- C_{max} of BI 425809 in plasma with and without co-administration of rifampicin (maximum measured concentration of the analyte in plasma)

5.2 SECONDARY ENDPOINTS

5.2.1 Key secondary endpoint

Not applicable.

5.2.2 Other Secondary endpoints

Secondary PK endpoints will be defined as in Section 5.5.1.2 of the CTP:

- $AUC_{0-\infty}$ of BI 425809 in plasma with and without co-administration of rifampicin (area under the concentration-time curve of the analyte in plasma over the time interval from 0 extrapolated to infinity)
- $t_{1/2}$ of BI 761036 in plasma without co-administration of rifampicin (terminal half-life of the analyte in plasma)

[figure not shown]
5.3 FURTHER ENDPOINTS

5.3.1 Safety endpoints

Safety and tolerability will be assessed by the frequency [N (%)] of subjects with drug-related AEs. Further criteria of interest will be:

- AEs (including clinically relevant findings from physical examination)
- Safety laboratory tests
- Vital signs (blood pressure, pulse rate)
- 12-lead ECG (occurrences of findings)

6. GENERAL ANALYSIS DEFINITIONS

6.1 TREATMENTS

For basic study information on treatments to be administered, assignment of treatment groups, and selection of doses, cf. Section 4 of the CTP.

Each subject is planned to be treated in two subsequent treatment periods. In the first treatment period, subjects will receive a single dose of 25 mg of BI 425809 (reference treatment, R). In the second treatment period, subjects will receive treatment with rifampicin 600 mg once daily over 10 days together with an administration of a single dose of 25 mg of BI 425809 on the seventh day of rifampicin treatment (test treatment, T). The sequence of these treatment periods is fixed and the same for all subjects.

For statistical analyses of AEs, laboratory tests, and vital signs, the following separate analysis phases will be defined for each subject:

Table 6.1: 1 Flow chart of analysis phases for statistical analysis of AEs, safety laboratory and vital signs

Study analysis phase	Label	Start	End
Screening	Screening	Date of informed consent at 12 a.m.	Date/time of first administration of BI 425809
On treatment BI 425809	BI 425809	Date/time of first administration of BI 425809	Minimum of date/time of first administration of BI 425809 + REP (11 days * 24 h) and first administration of loading RI
Follow-up BI 425809 ¹	F/U BI	Date/time of first administration of BI 425809 + REP (11 days * 24 h)	Date/time of first administration of loading RI
On treatment RI	Loading RI	Date/time of first administration of loading RI	Date/time of second administration of BI 425809
On treatment BI 425809+RI	BI 425809+RI	Date/time of second administration of BI 425809	Date/time of second administration of BI 425809 + REP (11 days * 24 h) or 12:00 a.m. on day after trial completion date, whichever occurs earlier
Follow-up BI 425809+RI ¹	F/U BI+RI	Date/time of second administration of BI 425809 + REP (11 days * 24 h)	12:00 a.m. on day after trial completion date
Post study ²	Post-study	12:00 a.m. on day after trial completion date	Not defined – a placeholder date is used, e.g. a date after database lock

¹ Follow-up phases might not exist, e.g. if loading RI is administered within 11 days of the time of administration of BI 425809, or the trial completion date is within 10 days of the time of administration of BI 425809+RI.

² AE tables will present results for the post-study phase only if at least one AE occurred in the post-study phase.

CTR Section 15, Appendix 16.1.9.2.8.2 and Appendix 16.1.9.2.8.3 AE displays will present results for the following study treatments during on-treatment phases:

- BI 425809
- Loading RI
- BI 425809+RI

Screening, follow-up and post-study periods will not be included in these sections/appendices.

In CTR Section 15 AE tables (but not in Appendix 16.1.9.2.8.2 and Appendix 16.1.9.2.8.3 AE tables), the following totals will be provided in addition:

- a total over the on-treatment phases of "BI 425809" and "BI 425809+RI" ("**Total BI**")
- a total over all on-treatment phases included in this analysis ("**Total on treatment**"). This includes all BI treatments and loading RI.

CTR Appendix 16.1.9.2.8.1 displays will present results for the screening, on-treatment, follow-up and post-study phases (post-study only if at least one AE occurred in the post-study phase).

Additionally to the totals defined above, the following total will be provided in CTR Section 16.1.9.2.8.1 AE tables:

- a total over all study phases ("**Total**")

Laboratory analyses will present results by treatment period (i.e., for treatment periods "BI 425809", "BI 425809+RI", and "Loading RI" plus "BI 425809+RI").

Analyses of vital signs will present results by BI 425809 treatment periods (i.e., for treatment periods "BI 425809", and "BI 425809+RI").

More details on the technical implementation of these analyses are provided in the ADS Plan of this TSAP.

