3.3.4 Removal of subjects from therapy or assessments

3.3.4.1 Removal of individual subjects

An individual subject is to be removed from the trial if:

1. The subject withdraws consent for trial treatment or trial participation, without the need to justify the decision
2. The subject needs to take concomitant drugs that interfere with the investigational product or other trial medication
3. The subject is no longer able to participate for other medical reasons (such as surgery, adverse events, or diseases)
4. The subject shows an elevation of AST and/or ALT ≥ 3 -fold ULN combined with an elevation of total bilirubin ≥ 2 -fold ULN (measured in the same blood sample) and/or needs to be followed up according to the 'DILI checklist' provided in the ISF.
5. The subject presents with a clinically relevant thrombocytopenia

A subject can also be removed from the trial if eligibility criteria are being violated or if the subject fails to comply with the protocol (for instance, by non-adherence to dietary rules, or non-attendance at study assessments).

If a subject is removed from or withdraws from the trial prior to first administration of trial medication, the data of this subject will not be entered in the case report form (CRF) or trial database and will not be reported in the clinical trial report (CTR). If a subject is removed from or withdraws from the trial after first administration of trial medication, this will be documented and the reason for discontinuation must be recorded in the CRF. In this case, the data will be included in the CRF/trial database and will be reported in the CTR. At the time of discontinuation a complete end of trial examination will be performed if possible and the information will be recorded in the CRFs. If the discontinuation occurs before the end of the REP (see [Section 5.2.2.2](#)), the discontinued subject should if possible be questioned for AEs and concomitant therapies at or after the end of the REP in order to ascertain collection of AEs and concomitant therapies throughout the REP, if not contrary to any consent withdrawal of the subject. These discontinuations will be discussed in the CTR.

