5.2.2.2 Adverse event collection and reporting

AEs collection

Upon enrolment into a trial, the subject's baseline condition is assessed (for instance, by documentation of medical history/concomitant diagnoses), and relevant changes from baseline are noted subsequently.

Subjects will be required to report spontaneously any AEs as well as the time of onset, end, and intensity of these events. In addition, each subject will be regularly assessed by the medical staff throughout the clinical trial and whenever the investigator deems necessary. As a minimum, subjects will be questioned for AEs (and concomitant therapies) at the time points indicated in the [Flow Chart](#). Assessment will be made using non-specific questions such as 'How do you feel?'. Specific questions will be asked wherever necessary in order to more precisely describe an AE.

[figure not shown]
A careful written record of all AEs shall be kept by the investigator in charge of the trial. Records of AEs shall include data on the time of onset, end time, and intensity of the event as well as any treatment or action required for the event and its outcome.

The following must be collected and documented on the appropriate CRF(s) by the investigator:

- From signing the informed consent onwards through the residual effect period (REP), until an individual subject's end of trial:
 - All AEs (serious and non-serious) and all AESIs.
 - The only exception to this rule are AEs (serious and non-serious) and AESIs in Phase I trials in healthy volunteers, when subjects discontinue from the trial due to screening failures prior to administration of any trial medication. In these cases, the subjects' data must be collected at trial site but will not be entered in the CRF or trial database and will not be reported in the CTR.

Proprietary confidential information © 2017 Boehringer Ingelheim International GmbH or one or more of its affiliated companies

- After the individual subject's end of trial:
 - The investigator does not need to actively monitor the subject for AEs but should only report relevant SAEs and relevant AESIs of which he may become aware of.

The REP for BI 425809, when measurable drug levels or pharmacodynamic effects are still likely to be present, is defined as 11 days after the last administration of BI 425809.

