Therefore, all AEs which occurred through the treatment phase and throughout the REP will be considered as on treatment; please see [Section 7.3.3](#). Events which occurred after the REP will be considered as post treatment events.

The follow-up period describes the period of time from the last administration of trial medication including the REP until the end of trial examination (last per protocol contact).

AE reporting to sponsor and timelines

The Investigator must report SAEs, AESIs, and non-serious AEs which are relevant for the reported SAE or AESI, on the BI SAE form via fax immediately (within 24 hours of awareness) to the sponsor's unique entry point (country specific contact details will be provided in the ISF). In specific occasions the Investigator could inform the sponsor upfront via telephone. The same timeline applies if follow-up information becomes available. This does not replace the requirement to complete and fax the BI SAE form.

With receipt of any further information to these events, a follow-up SAE form has to be provided. For follow-up information the same rules and timeline apply as for initial information.

Information required

For each AE, the investigator should provide the information requested on the appropriate CRF pages and the BI SAE form (if applicable). The investigator should determine the causal relationship to the trial medication.

The following should also be recorded as an (S)AE in the CRF and on the SAE form (if applicable):

Proprietary confidential information © 2017 Boehringer Ingelheim International GmbH or one or more of its affiliated companies

- Worsening of the underlying disease or of other pre-existing conditions
- Changes in vital signs, ECG, physical examination and laboratory test results, if they are judged clinically relevant by the investigator.

If such abnormalities already pre-exist prior trial inclusion they will be considered as baseline conditions.

All (S)AEs, including those persisting after individual subject's end of trial must be followed up until they have resolved, have been sufficiently characterised, or no further information can be obtained.

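### SAP Table 6.1: 1 cuts the BI 425809+RI on-treatment phase at the trial completion date, so an early completer's new AEs within the 11-day residual effect period can be classed as post-study

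*SAP*

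**What the plan says.** - **SAP 6.1, Table 6.1: 1, BI 425809+RI row.** The phase starts at the second BI 425809 dose and ends at that dose plus the REP of 11 x 24 h, "or 12:00 a.m. on day after trial completion date, whichever occurs earlier". Post-study starts at the same midnight.
- **Same table, BI 425809 row.** The end is "Minimum of date/time of first administration of BI 425809 + REP (11 days * 24 h) and first administration of loading RI". The trial completion date plays no part.
- **SAP 6.1, text below the table.** For CTR Section 15 and Appendices 16.1.9.2.8.2 and 16.1.9.2.8.3: "Screening, follow-up and post-study periods will not be included in these sections/appendices". Appendix 16.1.9.2.8.1 shows every phase and an all-phase total.
- **Protocol 5.2.2.2.** The REP is "defined as 11 days after the last administration of BI 425809", and "all AEs which occurred through the treatment phase and throughout the REP will be considered as on treatment".
- **Protocol 3.3.4.1.** For a subject who leaves early, "At the time of discontinuation a complete end of trial examination will be performed if possible". If this falls before the REP ends, the subject should, where possible and consistent with any withdrawal of consent, "be questioned for AEs and concomitant therapies at or after the end of the REP in order to ascertain collection of AEs".
- **Protocol 7.3.3.** Two successive allocation rules are given. The first runs treatment up to the next intake or the end-of-trial visit and does not mention the REP. The second runs treatment to the REP end. Both send events after the end-of-trial examination to post-study. The section then leaves the detailed intervals to the SAP.
- **SAP section 4.** It declares agreement with the protocol's methods and does not mention the cut.

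**The concern.** The REP is there because drug levels or effects are still likely during it, and an early end-of-trial examination does not change that. The protocol foresees a discontinuer examined before the REP is over and asks for the remaining REP events to be collected. The SAP table can then label those same events post-study, which removes them from the main AE tables and from the 'Total BI' and 'Total on treatment' columns.

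The endpoint at stake is the single safety endpoint named in SAP 5.3.1, the number and percentage of subjects with drug-related AEs. The two treatment columns also follow different rules, because only the combination row carries the cap. For a subject who leaves in period 1, the on-treatment phase and Post-study cover some of the same hours, so the table does not give a unique phase.

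**Working it through.** **Inputs**
- REP = 11 x 24 = 264 h (SAP Table 6.1: 1), which matches the 11 days in Protocol 5.2.2.2.
- Second BI 425809 dose on Day 1 at about 08:00; end-of-trial window Day 12 to Day 23 (Protocol Flow Chart).
- 16 subjects (Protocol synopsis and 3.3).
- Assumption: the trial completion date is the date of the end-of-trial examination. Neither document defines it.

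**Formulas.** REP end = Day 1 08:00 + 264 h = Day 12 08:00. For completion on Day d, the SAP cut is 00:00 on Day d+1, which is 24d - 8 hours after dosing. On-treatment time = min(264, 24d - 8). REP time moved to Post-study = max(0, 264 - (24d - 8)) = max(0, 272 - 24d).

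| Completion day | Cut (h after dose) | REP hours moved | Share of 264 h |
|---|---|---|---|
| 1 | 16 | 248 | 93.9% |
| 3 | 64 | 200 | 75.8% |
| 5 | 112 | 152 | 57.6% |
| 8 | 184 | 80 | 30.3% |
| 11 | 256 | 8 | 3.0% |
| 12 | 280 | 0 | 0% |

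The cap therefore bites only for completion on Day 11 or earlier. Completion on Day 12, the earliest scheduled day, puts the cut 280 - 264 = 16 h after the REP end, so on-schedule completers lose nothing. The shares are of time at risk, not of events.

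**Footnote 1 of the table.** It says a follow-up phase may not exist if completion falls within 10 days of the BI 425809+RI dose. Ten days after Day 1 is Day 11, the last day on which the cut (256 h) precedes 264 h. The SAP thus foresees completion dates inside the REP, and with the planned window these belong to early leavers.

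**Effect on the safety endpoint.** AEs are assigned by onset (Protocol 7.3.3) and counted by subject (SAP 7.8.1). If all 16 receive the second dose, one subject whose only drug-related AE in the phase starts in the gap changes the BI 425809+RI column by 1/16 = 6.25 percentage points. With an earlier drug-related AE in that phase, the column does not change. By the same subject-level counting, 'Total BI' changes only if the subject had no drug-related AE in either BI phase.

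**Overlap in period 1.** A subject who leaves on Day 3 of period 1 never takes rifampicin, so the BI 425809 phase runs to 264 h. On the same assumption about the completion date, Post-study begins at 64 h. The 200 h between belong to both phases.

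**After the change.** With the cap removed, the BI 425809+RI phase is 264 h for everyone given the second dose, and 0 REP hours go to Post-study.

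**The case against.** The best defence is that the SAP did what it was told. Protocol 7.3.3 twice sends events after the end-of-trial examination to post-study and delegates the intervals. A reader might infer an undeclared SAP deviation; the documents do not support that, because the conflict starts inside the protocol, between 5.2.2.2 and 7.3.3. What stands is that the SAP, as the place chosen to settle it, does so against 5.2.2.2 without saying so.

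Second, the trial completion date could mean the last contact, since 5.2.2.2 describes the end-of-trial examination as the last per-protocol contact and places it after the REP. If it meant the later REP questioning, the cap would not bite. Footnote 1 points the other way but does not settle it: a subject lost or withdrawing consent could also have an early date, with little collected afterwards. SAP 6.1 refers technical detail to an ADS Plan that is not among the documents.

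Third, a reader might infer that the AEs causing discontinuation are lost and the comparison is biased towards the combination. They are not: such an AE starts before discontinuation and stays on treatment. Nor is everyone who stops in period 2 affected. A subject who leaves during rifampicin loading never enters the capped phase. The displaced AEs also remain in Appendix 16.1.9.2.8.1 and its total, and the safety analysis is descriptive.

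These points narrow the problem, but do not remove the different rules for the two columns or the overlapping phases.

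**Conclusion.** The point holds in a narrow form. It needs a subject who took the second BI 425809 dose, whose trial completion date is Day 11 or earlier, and who has a new AE with onset after the cut but within 264 h of dosing. It rests on reading the trial completion date as the examination date, which is the more natural reading but is not stated. Such an AE leaves CTR Section 15 and the two on-treatment totals. The endpoint moves by 6.25 percentage points per subject in the combination column if that subject had no earlier drug-related AE in the phase. The documents give no expected number of such subjects, and there may be none.

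A general bias in favour of the combination does not follow. The asymmetry between rows is real. But how a period 1 discontinuer's overlapping hours would be resolved depends on programming that cannot be seen, and nothing shows that the combination column would lose events in practice. The overlap in the table needs correcting whichever rule is preferred.

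**What to change.** In SAP Table 6.1: 1:
1. Delete the completion-date cap from the BI 425809+RI row, so that the phase always ends at second dose + 264 h.
2. Start Post-study at the later of midnight after trial completion and the end of the REP after the subject's last BI 425809 dose.
3. For subjects who never reach the next administration, end the F/U BI and Loading RI rows at midnight after trial completion. As written, these rows close only at the first rifampicin dose and the second BI 425809 dose, so changing steps 1 and 2 alone would leave overlaps.
4. Define the trial completion date.

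In SAP section 4, record that the REP rule of Protocol 5.2.2.2 prevails over the end-of-trial cut in 7.3.3.

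The cost is a few table cells, a short statement and the matching programming. No new data are needed, because Protocol 3.3.4.1 already asks for these events where possible. The on-treatment AE count may come out slightly higher. If the completion date turns out to mean the later REP contact, the change alters no result for those subjects.
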